## Outcome Measures

### Primary Outcome Measures

#### *ECMO patients*

1. Difference of Cytokine response [ Time Frame: 6-24 hours ]

Level of pro- and anti-inflammatory cytokines (IL-1, IL-6, IL-8, IL-10, tumor necrosis factor-alfa) before initiation of ECMO, 2 hours after initiation ECMO support, at explantation of ECMO support, 6-12-24 hours after explantation of ECMO support.

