#### **4. Research methods and ethical issues**

Patients before implantation of ECMO and/or patients with sepsis will be enrolled in the study after giving a written, signed informed consent.

The participants will be randomized into 3 groups:

- **Intervention group #1** a cytokine adsorber will be used (30 patients): patients on ECMO – subgroup A; septic patients – subgroup B.
- **Intervention group #2** an extracorporeal hemoperfusion cartridge will be used (30 patients): patients on ECMO – subgroup C, septic patients – subgroup D.

- **Control group #3** without using extracorporeal adsorber (30 patients): patients on ECMO subgroup - E, septic patients - subgroup F.

The investigators will collect demographic, clinical and laboratory data about patients before, during and after the operation

The incidence of early cellular or humoral rejection, length of ventilation, ICU and hospital stay, the use of vasopressors and inotropes in the perioperative period and incidence of perioperative complications and survival will be documented.

The level of cytokines (IL-1, IL-6, IL-8, IL-10, tumor necrosis factor-alfa) and complements before, during and after the use of ECMO, patients with sepsis will be determined if the investigators find relevant difference between the two groups in clinical variables.

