### Study Design

Study Type: Interventional (Clinical Trial)

Estimated Enrollment: 90 Participants

Allocation: randomized

Interventional Model: Parallel assignment

Masking: None (Open Label)

Experimental (subgroups)	Intervention / treatment (device)
Cytokine adsorber filter will be installed into the (hemodialysis or cardiopulmonary bypass (CPB) (15 patients on ECMO)	Cytokine adsorber is a biocompatible, high adsorptive polymer indicated in conditions where cytokine levels are extremely elevated.
Cytokine adsorber filter will be installed into the (hemodialysis or cardiopulmonary bypass (CPB) (15 patients with sepsis)	Cytokine adsorber is a biocompatible, high adsorptive polymer indicated in conditions where cytokine levels are extremely elevated.
Extracorporeal hemoperfusion cartridge will be installed into the (hemodialysis or cardiopulmonary bypass (CPB) (15 patients on ECMO)	Extracorporeal hemoperfusion cartridge is a biocompatible, high adsorptive polymer indicated in conditions where cytokine levels are extremely elevated.
Extracorporeal hemoperfusion cartridge will be installed into the (hemodialysis or cardiopulmonary bypass (CPB) (15 patients with sepsis)	Extracorporeal hemoperfusion cartridge is a biocompatible, high adsorptive polymer indicated in conditions where cytokine levels are extremely elevated.
Control (subgroups)	
No filter will be installed into the ECMO in	

this study group (15 patients)	
No filter will be installed into the patient with sepsis (15 patients)	

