#### Secondary outcomes

1. Ventilator free days (VFD) [Time Frame: 30 days]

Ventilator free days (VFD) in the first 30 days after randomization, where invasive mechanical ventilation (IMV), non-invasive ventilation (NIV) and ECMO are defined as ventilator days. VFD=0, if the patient dies in the first 30 days after randomization

2. Time to extubation from ventilation and explantation from ECMO [ Time Frame: 30 days ]

Time to extubation from ventilation and explantation from ECMO. Death under ventilation and/or ECMO will be analyzed as a competing event. The time will be censored at the time of last visit for surviving patients under ventilation and/or ECMO.

3. Difference of d-dimers [Time Frame: 24, 48, 72 hours]

Comparison to enrollment or between 3 groups at 24, 48, 72 h

4. Difference of Serum lactate [Time Frame: 24, 48, 72 hours]

Comparison to enrollment or between 3 groups at 24, 48, 72 h

5. SOFA-Score [Time Frame: 24, 48, 72 hours]

Sequential Organ Failure Assessment Score at 24, 48, 72 h (values from 6 to 24, where the higher values explain higher disease severity)

6. Serious adverse device effects [Time Frame: 30 days]

Serious complications or malfunctions related to the CytoSorb device

7. Adverse event of special interest: air in the ECMO system [Time Frame: 30 days]

- Unintended air in the ECMO system during operation of the device
- 8. Adverse event of special interest: blood-clotting in the ECMO system [Time Frame: 30 days]
  - Unintended blood-clotting in the ECMO system during operation of the device
- 9. Adverse event of special interest: bleeding complications [Time Frame: 30 days]
  - Major bleeding events

*Patient with septic shock*

- 1. Difference of Cytokine response [ Time Frame: 24-48 hours of septic shock ]
  - Cytokine response: Level of procalcitonin, Level of C-reactive protein, Level of interleukin-1, Level of interleukin-6, Level of interleukin-8, Level of interleukin-10, Level of Tumor Necrosis Factor-  $\alpha$  at 24, 48 hours.

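### ECMO primary outcome: four of six cytokine samples are tied to explantation, so the late comparison is in selected patients at unequal times, and the assays themselves are conditional

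*Combined protocol and SAP*

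**What the plan says.** All references are to the combined protocol and SAP.

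- **Outcome Measures, ECMO patients.** The primary outcome is headed "Difference of Cytokine response [ Time Frame: 6-24 hours". Five cytokines are measured before ECMO starts, 2 hours after it starts, and then "at explantation of ECMO support, 6-12-24 hours after explantation of ECMO support". No one time point or cytokine is named as primary.
- **Secondary outcomes, item 2.** Time to extubation and explantation is analysed over 30 days. "Death under ventilation and/or ECMO will be analyzed as a competing event". For survivors still supported, "The time will be censored at the time of last visit for surviving patients under ventilation and/or ECMO". Item 1 sets ventilator-free days to zero at death. These rules are written for those two outcomes only.
- **Section 4, Research methods and ethical issues.** "Patients before implantation of ECMO and/or patients with sepsis will be enrolled in the study". Cytokines are planned "before, during and after the use of ECMO", but they "will be determined if the investigators find relevant difference between the two groups in clinical variables".
- **Study Design.** "Masking: None (Open Label"; 15 ECMO patients in each of three arms.
- **Statistical studies.** Quantitative data are compared by Mann-Whitney and t-tests. Nothing is said about deaths, missing values or differing sampling times.

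**The concern.** Randomisation protects a comparison of everyone randomised at a common time. It does not protect a comparison limited to patients who reached a later event, each sampled on whatever day it happened. Explantation is such an event. The adsorbers may influence it, and it is decided by staff who know the allocation.

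Three things follow:

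1. Patients who die on ECMO or stay on it contribute no late samples, which shrinks arms of only 15.
2. If the arms lose different patients, those left are no longer comparable.
3. If time on ECMO differs between arms, the arms are sampled at different stages of illness even when death rates are equal.

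The conditional assay in section 4 adds a further risk. The primary outcome might never be measured, or might be measured only after clinical results have been seen.

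**Working it through.** **Step 1. Count the times.** Six are listed: before ECMO; 2 h after start; explantation; and 6, 12 and 24 h after explantation. Four of the six are tied to explantation. The figures 6 and 24 in the time frame occur in this outcome only as hours after explantation. Those post-explantation samples require a patient alive and off ECMO. The sample at explantation is less certain: the term is not defined, so one might be drawn if the circuit is removed at death.

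**Step 2. Look for a rule.** The plan foresees deaths on ECMO and survivors still on ECMO, but only for ventilator-free days and time to explantation. Neither the primary outcome nor the statistics section says how such patients enter the cytokine comparison.

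**Step 3. Loss of patients.** The plan has no sample-size figure to reproduce. Assumptions: two-sided t-test, alpha 0.05, a true 1 SD difference, and a share q never reaching explantation. Late n per arm = 15(1 − q).

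| q | Late n per arm | Power |
|---|---|---|
| 0% | 15 | 75% |
| 30% | 15 × 0.7 = 10.5 | 59% |
| 50% | 15 × 0.5 = 7.5 | 43% |
| 60% | 15 × 0.4 = 6 | 35% |

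**Step 4. Unequal timing.** Assumed model: log cytokine = −b × days on ECMO + N(0,1); lognormal ECMO time with coefficient of variation 0.6, drawn independently of cytokine level; 10 per arm; 20,000 runs. Spurious difference = b × difference in mean days.

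| b (SD per day) | Mean days, device vs control | Spurious difference | False positives | Power for true 1 SD benefit |
|---|---|---|---|---|
| 0 | equal | 0 | 5% | 56% |
| 0.1 | equal (6, 7 or 8) | 0 | 5% | 52%, 49%, 48% |
| 0.05 | 6 vs 7 | 0.05 × 1 = 0.05 SD | 5% | about 50% |
| 0.1 | 6 vs 8 | 0.1 × 2 = 0.2 SD | about 7% | about 35% |
| 0.2 | 6 vs 9 | 0.2 × 3 = 0.6 SD | about 15% | about 11% |

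The fair contrast for the 6 vs 8 day row is 48-52%, not 56%. The fall from 56% to 48-52% comes from the spread of ECMO time within arms, which is present even when the arms do not differ. Reversing the arms reverses the sign of the spurious difference.

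**Step 5. Selection by death alone.** With 50% against 30% deaths, and an odds ratio for death of 2.0, 2.7 or 4.5 per SD of cytokine, the survivors' means differ by 0.12, 0.16 or 0.20 SD with no true effect. At equal death rates the shift is zero.

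**Step 6. Would a fixed 24 h sample lose fewer patients?** Enrolment precedes ECMO. So anyone alive 24 h after explantation was also alive 24 h after randomisation and 24 h after ECMO start. The fixed sample therefore cannot lose more patients to death. If a share f of those never explanted die in the first 24 h, n at 24 h = 15(1 − qf). With q = 50%:

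| f | n at 24 h | Power at 1 SD |
|---|---|---|
| 10% | 15 × 0.95 = 14.25 | 73% |
| 25% | 15 × 0.875 = 13.125 | 69% |
| 50% | 15 × 0.75 = 11.25 | 62% |
| 100% | 15 × 0.5 = 7.5 | 43% |

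The late sample gives 43% throughout. The effects at the two times are different quantities: the late effect would have to be 1.44, 1.37, 1.26 or 1.00 SD to match 1 SD at 24 h.

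**The case against.** **The response after ECMO is a legitimate question.** Section 4 plans samples after support as well as before and during it, and a rule for deaths and non-explanted patients would close the missing-rule gap. That is so, and it is why the explantation samples should be kept. A rule alone would not cure the unequal timing.

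**The bias may be small.** This stands in part. In the central case the false-positive rate is about 7% against 5%. The 15% figure needs the top of both assumed ranges, and selection by death is modest.

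**A reader might infer that the bias always works against the arm that comes off earlier.** The documents do not support this. The direction in step 4 assumes that ECMO time is independent of cytokine level. If patients come off when they recover, the two are linked, and sign and size may differ.

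**A reader might also infer that the plan ignores death altogether, or that the whole primary outcome is compromised.** Neither follows. Rules for death exist for two secondary outcomes, and the samples before ECMO and at 2 h are not tied to explantation.

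**A clock from randomisation has its own gap.** This stands. The interval from randomisation to ECMO or adsorber start is not stated. Section 4 enrols before implantation, while the eligibility table describes ICU patients with ECMO; if patients already on ECMO may enter, even the baseline sample is in doubt.

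**Conclusion.** The concern holds and should be fixed. As written, the late between-arm comparison is made in patients selected after randomisation and at unequal times, with no rule for those who die on or stay on ECMO. This much rests on the text alone. Separately, section 4 leaves it open whether the primary cytokines will be measured at all, and whether that is decided after clinical results are seen.

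The size is illustrative, because the documents give no ECMO mortality, rate of cytokine change, alpha or effect size. Loss of patients is the clearest cost: power of 59%, 43% or 35% instead of 75% if 30%, 50% or 60% never reach explantation. Unequal timing could add a spurious 0.05 to 0.6 SD over the range considered (0.05-0.2 SD per day, 1-3 days), with false-positive rates of 5-15%, subject to the independence assumption. Unequal deaths add up to about 0.2 SD. These figures show that the result would be hard to interpret; they do not show that it would be wrong.

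**What to change.** 1. **Fixed-time primary comparison.** Add one cytokine draw at 24 h in all ECMO arms, on a stated clock, and make it the primary between-arm comparison for one cytokine named in advance. Draws at 48 and 72 h are optional and supportive; d-dimers, lactate and SOFA already use that grid. The clock may start at randomisation or at ECMO start. If at randomisation, state and record the interval to ECMO and adsorber start. Reconcile section 4 with the eligibility table on whether patients enter before or after ECMO begins.
2. **Explantation samples.** Keep them as secondary, descriptive data, reported with days since randomisation and, by arm, the numbers who died on or stayed on ECMO.
3. **Deaths.** Analyse measured values in patients alive at 24 h, say that this is still conditional on survival, and report deaths before 24 h by arm. Add a sensitivity Mann-Whitney test with death ranked worst, for a primary cytokine whose harmful direction is clear. Ranking death worst costs power (with 15 per arm and 1 SD: 60% against 69% on measured values at 5% deaths, 51% against 65% at 10%), so it should not be the main analysis.
4. **Assays.** Reconcile section 4 with the primary outcome so that the primary cytokines are measured in all ECMO patients whatever the clinical results.

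**Cost.** Protocol wording and a revised sampling sheet. Draws per patient rise from 6 to 7: 3 × 15 = 45 more samples and 45 × 5 = 225 more assays, or none if an explantation draw is swapped out. The main downside is that the response after ECMO is no longer the primary comparison.

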#### Secondary outcomes

1. Ventilator free days (VFD) [Time Frame: 30 days]

Ventilator free days (VFD) in the first 30 days after randomization, where invasive mechanical ventilation (IMV), non-invasive ventilation (NIV) and ECMO are defined as ventilator days. VFD=0, if the patient dies in the first 30 days after randomization

2. Time to extubation from ventilation and explantation from ECMO [ Time Frame: 30 days ]

Time to extubation from ventilation and explantation from ECMO. Death under ventilation and/or ECMO will be analyzed as a competing event. The time will be censored at the time of last visit for surviving patients under ventilation and/or ECMO.

3. Difference of d-dimers [Time Frame: 24, 48, 72 hours]

Comparison to enrollment or between 3 groups at 24, 48, 72 h

4. Difference of Serum lactate [Time Frame: 24, 48, 72 hours]

Comparison to enrollment or between 3 groups at 24, 48, 72 h

5. SOFA-Score [Time Frame: 24, 48, 72 hours]

Sequential Organ Failure Assessment Score at 24, 48, 72 h (values from 6 to 24, where the higher values explain higher disease severity)

6. Serious adverse device effects [Time Frame: 30 days]

Serious complications or malfunctions related to the CytoSorb device

7. Adverse event of special interest: air in the ECMO system [Time Frame: 30 days]

- Unintended air in the ECMO system during operation of the device
- 8. Adverse event of special interest: blood-clotting in the ECMO system [Time Frame: 30 days]
  - Unintended blood-clotting in the ECMO system during operation of the device
- 9. Adverse event of special interest: bleeding complications [Time Frame: 30 days]
  - Major bleeding events

*Patient with septic shock*

- 1. Difference of Cytokine response [ Time Frame: 24-48 hours of septic shock ]
  - Cytokine response: Level of procalcitonin, Level of C-reactive protein, Level of interleukin-1, Level of interleukin-6, Level of interleukin-8, Level of interleukin-10, Level of Tumor Necrosis Factor-  $\alpha$  at 24, 48 hours.

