## **2. General project concept**

### **2.1. Introduction**

Principal Investigator – [name], Chief of Cardiac Surgery Department of JSC "National Research Center for Cardiac Surgery" (hereinafter referred to as JSC NNCS).

JSC "National Research Center for Cardiac Surgery" is a research center that implements a program for treating patients with chronic heart failure (CHF) and pulmonary failure (PF) at the terminal stage, including orthotopic transplantation of the heart and lungs, mechanical support of the blood circulation.

The implementation of this project will improve the effectiveness of surgical treatment and reduce the level of complications and mortality among patients with heart failure and heart failure in the terminal stage.

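### Time to extubation and explantation counts a patient taken off both ventilation and ECMO who then dies as reaching the favourable event, where ventilator-free days score 0

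*Combined protocol and SAP*

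**What the plan says.** Both outcomes stand in the list of secondary outcomes for ECMO patients.

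- **Item 2, event.** The outcome is headed "Time to extubation from ventilation and explantation from ECMO [ Time Frame: 30 days", and its definition repeats the same words. It sets no condition on why support was removed, how long the patient must stay off it, or whether the patient survives.
- **Item 2, competing event.** "Death under ventilation and/or ECMO will be analyzed as a competing event".
- **Item 2, censoring.** "The time will be censored at the time of last visit for surviving patients under ventilation and/or ECMO".
- **Item 1 (VFD), death rule.** "VFD=0, if the patient dies in the first 30 days after randomization". This applies whether or not the patient was on support at death.
- **Item 1 (VFD), support definition.** "invasive mechanical ventilation (IMV), non-invasive ventilation (NIV) and ECMO are defined as ventilator days".

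The design table in section 4 allots "15 patients on ECMO" to each adsorber arm and 15 ECMO patients without a filter to the control arm. The trial is open label.

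**The concern.** An outcome of this kind is read as speed of liberation: a higher or earlier curve looks better. As written, the curve also rises when both supports are stopped because treatment has failed. If the patient then dies, even hours later, the death is not a death on support. It comes after the event and changes nothing in the analysis.

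Stopping support is a bedside decision made by staff who know the allocation. If one arm has more such withdrawals, or earlier ones, that arm will appear to come off support faster without any more patients recovering. The VFD outcome beside it scores these patients 0, so a report could show two liberation outcomes pointing in different directions, with no explanation in the plan.

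**Working it through.** The documents give no event rate, effect size or power for this outcome, so there is no planned figure to reproduce. The check applies the written rules to each possible state, then does the arithmetic per patient. I assume both outcomes run from randomization; item 2 does not name its starting point.

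**Step 1. Classify each state under both rules.** Support is the status at death, or at the end of follow-up for survivors.

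| ECMO | Ventilation | By day 30 | Item 2 | VFD |
|---|---|---|---|---|
| on | on | alive | censored | still supported |
| on | on | dead | competing | 0 |
| on | off | alive | censored | still supported |
| on | off | dead | competing | 0 |
| off | on | alive | censored | still supported |
| off | on | dead | competing | 0 |
| off | off | alive | event | above 0 |
| **off** | **off** | **dead** | **event** | **0** |

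Seven of the eight states are compatible. Only the last is discordant: item 2 records the favourable event and VFD gives the worst score.

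**Step 2. Effect per patient.** Inputs: n = 15 ECMO patients per arm (design table, section 4); k = patients in an arm who come off both supports and die by day 30. The documents do not give k, so the values below are assumptions.

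Shift in 30-day cumulative incidence = k / n.

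| k (assumed) | Shift |
|---|---|
| 1 | 1/15 = 6.7 points |
| 2 | 2/15 = 13.3 points |
| 3 | 3/15 = 20.0 points |
| 4 | 4/15 = 26.7 points |

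**Step 3. Illustration.** Suppose 6 of 15 patients are alive and liberated at day 30 and k = 2. The written rule gives (6 + 2)/15 = 53.3%. Counting only those alive and liberated gives 6/15 = 40.0%. The gap is 13.3 points. The contrast between two arms moves by the same amount if k differs by 2 between them.

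**Step 4. Does another section settle the coding?** No. Statistical studies names Kaplan-Meier and Cox regression only; it gives no competing-risk estimator and no rule for death after removal of support.

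**The case against.** The strongest reply is that the rule is complete for the event it names. Any death before both supports are off is a death on at least one of them, and a death after the event cannot compete with it. The plan never calls the event success or recovery. On this view the criticism asks for a different outcome, and all-cause death is visible anyway through VFD and through overall survival under Other Pre-specified Outcomes. The logic is sound, and the other outcomes do limit the harm. They do not correct this curve, which will still be read as liberation.

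A reader might also infer more than the documents support:

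- **That withdrawing either support before death counts as the event.** It does not. Both must be removed, and the and/or wording makes death on the remaining one a competing event.
- **That item 2 contradicts the VFD rule.** Two outcomes may use different death rules. This is an inconsistency, confined to one state and given no reason in the plan.
- **That exchange to another device, or transplantation, puts the two outcomes in conflict.** The pathway is plausible, since section 2.1 describes the centre's programme as "including orthotopic transplantation of the heart and lungs, mechanical support of the blood circulation". But VFD does not mention these either. A survivor who is then off ECMO and ventilation meets the event and also accrues ventilator-free days, so the outcomes agree. This is an omission in both.
- **That extubation to non-invasive ventilation, or a brief period off support, is definitely scored as the event.** Item 2 does not say whether ventilation includes non-invasive ventilation, nor how re-intubation or re-cannulation is handled. Either reading is an inference from silence.
- **That the overstatement can be put at a definite size.** Any range for the total rests on assumed counts; only the shift per patient is exact.

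**Conclusion.** The concern holds for one state. A patient removed from both ventilation and ECMO who then dies is counted as reaching the favourable event in item 2, and has VFD of 0 if death is by day 30. Each such patient moves the 30-day cumulative incidence by 6.7 points in an ECMO group of 15. The total effect is unknown because the documents give no frequency of withdrawal followed by death, and nothing shows that the arms will differ in it. The open-label design leaves that possibility open but does not establish it.

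This affects one secondary outcome, not the primary cytokine comparison. It is worth correcting because the correction is cheap and the written rule can mislead.

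**What to change.** 1. Define the event as the first time the patient is alive and free of invasive ventilation, non-invasive ventilation and ECMO, which is the support definition VFD already uses, and remains so for a short prespecified period, for example 48 h. This also settles the non-invasive ventilation question and support resumed within the period.
2. Count any death before that condition is met as the competing event, including death after support has been withdrawn.
3. Add a sensitivity analysis that treats every death by day 30 as failure. It is needed because a patient who stays off support for the chosen period and dies later, still within 30 days, would remain an event in the main analysis but have VFD of 0.
4. Report by arm the number of explantations to another device or to transplantation, since neither outcome addresses them.
5. State how removals close to day 30 are handled when the period cannot be completed within the time frame.

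**Cost.** This is mainly endpoint wording. VFD already needs days on support and death by day 30, and overall survival needs the date of death. A period set in hours would also need times, or could be written in whole days. Item 4 needs the reason for explantation to be recorded; no case report form is shown, so it may already be collected. The reported liberation rate will be somewhat lower, and the length of the period is a choice that the documents do not inform, so it should be fixed before the data are examined.

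### Secondary outcome 6 counts serious device effects for one named product although two devices are randomised, so one device has no such count; septic patients probably have it for neither

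*Combined protocol and SAP*

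**What the plan says.** Section 4 (Research methods and ethical issues) sets up two device groups and a control group. In group 1 "a cytokine adsorber will be used (30 patients"); in group 2 "an extracorporeal hemoperfusion cartridge will be used (30 patients"). The Study Design table in the same section splits each group into 15 ECMO and 15 septic patients. It lists the two devices in separate rows, for example "Extracorporeal hemoperfusion cartridge will be installed into the (hemodialysis or cardiopulmonary bypass (CPB) (15 patients with sepsis").

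Under Outcome Measures, the ECMO heading is followed by a primary outcome and nine secondary outcomes. Item 6 has a device-neutral title and a 30-day time frame, and is defined as "Serious complications or malfunctions related to the CytoSorb device". The adjoining safety items are:

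- item 7, "Unintended air in the ECMO system during operation of the device";
- item 8, "Unintended blood-clotting in the ECMO system during operation of the device";
- item 9, "Major bleeding events".

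A septic-shock heading then restarts the numbering at 1. It is followed by its own secondary list of five items, all laboratory markers. Other Pre-specified Outcomes adds overall survival over 30 days and mortality in the first 72 hours. Section 4 also says that "incidence of perioperative complications and survival will be documented".

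**The concern.** The title of item 6 promises a safety outcome for study devices in general, but the definition delivers it for one product. The trial is open label, so staff know which device each patient received. A definition tied to a product name therefore invites recording for that product alone. If attribution is not recorded at the time for the other device, it is hard to reconstruct later.

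Both devices are objects of study in both cohorts: Subtasks 1.2 and 2.2 of section 2.3 concern the adsorber, and 1.3 and 2.3 the cartridge. Section 8 (Expected results) intends the data to underpin practical protocols for ECMO and for septic patients. Under the definition as written, the ECMO protocol would rest on serious-device-effect data for one device of two. If item 6 is confined to the ECMO cohort, the septic protocol would have such data for neither.

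**Working it through.** **Inputs.** Three groups of 30 and six subgroups of 15 (section 4 and its Study Design table), and the wording and position of item 6 (Secondary outcomes). The documents give no device-event rate, so no expected number of events is calculated.

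**The plan's own figure.** 3 × 30 = 90 and 6 × 15 = 90, which agrees with the stated enrolment of 90. Control patients have no adsorption device and cannot contribute to item 6, so the relevant denominator is 2 × 30 = 60 device-treated patients.

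**Which device is covered.** CytoSorb appears nowhere else in the supplied text, and no passage links it to a group. Taking it as one of the two study devices, the other is uncovered whichever it is. Because the groups have the same size, the counts below do not depend on the identification.

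**Which cohort is covered.** Item 6 follows the ECMO heading, items 7 and 8 concern the ECMO system, and the septic-shock heading restarts the numbering and has its own list. The ECMO-only reading is therefore the likelier one. Heading levels in the extracted text are not fully clear, so both readings are shown.

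| Item 6 | Cohorts | Named product | Other device | Covered of 60 |
|---|---|---|---|---|
| As written | ECMO only (likelier) | 15 | 0 | 15 (25%) |
| As written | Both | 30 | 0 | 30 (50%) |
| Both devices named | ECMO only | 15 | 15 | 30 (50%) |
| Both devices named | Both | 30 | 30 | 60 (100%) |

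**Two separate gaps.** On the ECMO-only reading, 60 − 15 = 45 device-treated patients lie outside item 6. The product name accounts for 15 of them (ECMO patients on the other device). The absence of an equivalent septic item accounts for the other 30 (15 per device).

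**Whether other items fill the gap.** Items 7 and 8 record particular circuit events, and 'the device' in them may mean the ECMO system or the adsorber. Item 9, survival and mortality are not attributed to a device. Perioperative complications are neither defined nor attributed. None of these yields a count of serious device-related events.

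**Precision after repair.** With zero events in n patients, the exact one-sided 95% upper bound is 1 − 0.05^(1/n).

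- n = 15: 1 − 0.05^(1/15) = 0.181, or 18.1%.
- n = 30: 1 − 0.05^(1/30) = 0.095, or 9.5%.

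The upper limits of the two-sided 95% exact interval, 1 − 0.025^(1/n), are 21.8% and 11.6%. As written, the uncovered device has no denominator and so no bound.

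**The case against.** The strongest reply is that this is a leftover product name, not a decision to leave a device out. The title of item 6 is generic, the rest of the plan uses generic device names, and one bibliography entry has a trade-mark sign after the generic words, which fits an incomplete replacement of a brand name. A site might simply record by the title. This is plausible, and a reader should not infer that the sponsor chose to exclude a device: nothing in the documents shows that. But the definition, not the title, decides what is counted, and the two disagree.

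A second reply is that harm is captured elsewhere. That is partly right. A reader might infer that one device group would have no safety data; the documents do not support this, because bleeding, survival, mortality and perioperative complications are recorded without reference to a product, and items 7 and 8 can be read that way. What is missing is the device-attributed count.

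A third reply is that groups of this size could not separate the two devices on rare events. That is accepted. It is why the remedy is descriptive, but it does not justify having no count for one device.

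**Conclusion.** The point holds as an inconsistency between the title of item 6, its definition and the randomised groups. One of the two devices has no serious-device-effect count. On the likelier ECMO-only reading, item 6 covers 15 of 60 device-treated patients and septic patients have the count for neither device; on the wider reading it covers 30 of 60.

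The result assumes only that CytoSorb is one of the two study devices. It is tempting to say outright that the hemoperfusion cartridge is the one left out, with 0 of its 30 patients covered. That follows only if CytoSorb is the group 1 adsorber. The arm names and the trade-mark sign suggest so, but the documents never say it.

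The allocation, the sample size and the primary cytokine outcome are unaffected. The item should be corrected because the gap is in a safety definition, is cheap to close now and is hard to repair afterwards.

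**What to change.** 1. Define item 6 as any serious complication or malfunction attributed to the cytokine adsorber or to the hemoperfusion cartridge.
2. State that it applies to ECMO and to septic patients, over the same 30 days.
3. Report counts with exact intervals by device and cohort, with no between-device test.
4. In items 7 and 8, state whether 'the device' means the ECMO system or the adsorber or cartridge.

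The cost is a change to the outcome list and some extra data entry. On the ECMO-only reading, item 6 would be recorded for 15 + 30 = 45 more patients: 15 from naming both devices and 30 from adding the septic cohort. If it was already meant for both cohorts, the extra number is 60 − 30 = 30.
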